9.10 Pharmacodynamic Analysis (Optional)

As a marker of the effects of PD-0325901, ERK phosphorylation will be measured in dermal neurofibromas using methods described by [name] et al. Dermal neurofibromas are nerve tumors associated with dermal and epidermal nerves. Many NF1 patients develop dermal neurofibromas around the time of puberty. The cellular composition of dermal neurofibromas is indistinguishable from that of plexiform neurofibromas; therefore, dermal neurofibromas may be useful as an accessible surrogate tissue for analysis of therapeutic efficacy.

Three millimeter punch biopsies of 1-2 dermal neurofibromas (2 dermal neurofibromas per timepoint is preferred) will be made prior to initiating therapy with PD-0325901 and during week 3 of course 1 at least 30 min but no more than 6 hours after taking the morning dose. At each time point, one tumor will be fixed in formalin for paraffin embedding, and shipped on wet ice. At the same time, one tumor will be frozen in liquid nitrogen and stored at -80°C and shipped separately, on dry ice. If only one tumor is biopsied, the sample should be placed in formalin. Time of tumor removal after drug dose will be noted. Any remaining specimens will be stored for future research with subject consent. Details regarding sample processing and shipment are provided in Appendix VI.

9.11 Plasma Cytokines and Growth Factors (Optional)

Procedure: 10 ml blood will be drawn into EDTA tubes before treatment initiation, during week 3 of course 1 and during week 3 of course 4. The sample will be collected at least 30 min but no more than 6 hours after taking the morning dose. Any remaining specimens will be stored for future research with subject consent.

9.12 Maximum blood volumes for pharmacokinetic and pharmacodynamic studies

Institutional guidelines will be followed for maximum blood volumes for research samples. The table below provides details regarding blood volumes obtained for research studies during course 1. All subjects should have blood samples obtained for pharmacokinetic analysis.

Type of test	Volume per sample (ml)	Number of samples (volume for all samples, ml)
Pharmacokinetics	3	9 (27)
Plasma Cytokine Measurement	10	3 (30)
Total volume for research samples course 1		12 (57)

9.13 Quality of Life and Pain Evaluations (Required)

This study will evaluate quality of life, pain intensity, and pain interference in subjects during treatment with PD-0325901. The Pediatric Quality of Life Inventory (PedsQL) NF1 Module (Adult and Teen self-report forms) will be used to assess disease-specific QOL. Pain intensity will be assessed by self-report with the Numeric Rating Scale-11 (NRS-11) and pain interference will be measured by the Brief Pain Inventory (BPI) Pain Interference Scale. The following table summarizes the quality of life and pain questionnaires to be completed by age of the subjects.

Quality of Life and Pain Questionnaires to be Completed by Age of Subject at Study Entry

Questionnaire	Age of Subject (years) at Study Entry	
	16-20*	21+*
Disease Specific QOL		
Subject: PedsQL NF1 Module-Teen or PedsQL NF1 Module-Adult	X	X
Pain		
		Age of Subject (years)
		16+**
Subject: NRS-11 Pain Intensity and BPI-Pain Interference	X	X

Background Information Forms to be Completed by the Subject

Questionnaire	Age of Subject (years)
	16+**
Background Information	
All subjects QOL Background Form	X

*If subjects are 21 years old at study entry, they should be administered the Adult PedsQL NF1 Module. If subjects are 16 to 20 years old at study entry, they should be administered the Teen PedsQL NF1 Module. However, if subjects turn 21 years old during the study, they should continue to be administered the Teen version of this scale that they started at study entry.

**All subjects should complete the same self-report pain intensity and pain interference measures and background form.

To allow for more meaningful analysis of the QOL data, the subject (≥ 16 years) also will complete a self-report background information form at study entry and each QOL assessment. This form will collect general information such as their level of education, work status, psychiatric diagnoses, and pain medications, as well as the visibility of NF1 tumors and severity of NF1 symptoms.

These forms should be completed pre-treatment, after course 4 ± 2 weeks, 8 ± 2 weeks, 12 ± 2 weeks, 18 ± 2 weeks, and 24 ± 2 weeks. In addition, at the end of treatment ± 2 weeks if this is not encompassed in the times above. When administering these forms, review the instructions with the subjects and check to make sure they answered all the items. If subjects have difficulty reading, it is permissible to read the items to them, but the subjects should answer the items themselves. Completed forms should be sent (fax or mail copies) to the NF Consortium Operations Center within 2 weeks of completion. For any questions regarding the QOL/pain assessment please contact: [name] at [contact]. See Appendix VII for a description of the QOL and pain measures.

The QOL documents will be reviewed centrally by [name]. If any responses are noted that suggest serious emotional distress, the PI at the subject's site will be

notified. The site PI will be responsible for acknowledging to [name] receipt of these concerns and for initiating appropriate action as deemed clinically necessary.

10.0 ADVERSE REPORTING REQUIREMENTS

10.1 Definitions

- **Adverse Events:** An adverse event is any new, undesirable medical occurrence or change (worsening) of an existing condition in a subject that occurs during treatment, whether or not considered to be product related. Therefore, adverse events are treatment emergent signs or symptoms. Elective hospitalizations for pretreatment conditions (e.g., elective cosmetic procedures) are not adverse events. Non-clinically significant abnormal laboratory values should not be reported as adverse events; however, any clinical consequences of the abnormality should be reported as adverse events. All adverse events must be noted on the case report forms and submitted to the operations center within 2 weeks of completion of every treatment course.

For all adverse events, the investigator must pursue and obtain information adequate both to determine the outcome of the adverse event and to assess whether it meets the criteria for classification as a serious adverse event requiring immediate notification (within 24 hours) to the site PI and clinical coordinator, as well as the NF Operations Center. Follow-up of the adverse event, even after the date of therapy discontinuation, is required if the adverse event or its sequelae persist. Follow-up is required until the event or its sequelae resolve or stabilize at a level acceptable to the investigator and sponsor.

- **Serious Adverse Events:** A serious adverse event is defined by regulatory agencies as one that suggests a significant hazard or side effect, regardless of the investigator's or sponsor's opinion on the relationship to investigational product.

This includes, but may not be limited to, any event that (at any dose):

is FATAL

is LIFE THREATENING (places the subject at immediate risk of death);

requires HOSPITALIZATION or prolongation of existing hospitalization;

is a persistent or significant DISABILITY/INCAPACITY; or

is a CONGENITAL ANOMALY/BIRTH DEFECT

Important medical events that may not be immediately life threatening or result in death or hospitalization, but may jeopardize the subject or require intervention to prevent one of the outcomes listed above, or result in urgent investigation, may be considered serious. Examples include allergic bronchospasm, convulsions, and blood dyscrasias. A planned medical or surgical procedure is not, in itself, an SAE.

10.2 Common Terminology Criteria for Adverse Events (CTCAE)

This study will utilize the CTCAE of the National Cancer Institute for reporting and grading of adverse events. A copy of the current version of the CTCAE version 4.0 can be downloaded from the CTEP home page: <http://ctep.cancer.gov/reporting/ctc.html>

10.3 Attribution: Definitions of relationship to study medication are as follows:

- UNRELATED: bears no relation to timing of medication, similar to symptoms or signs expected in the disease process, does not recur on rechallenge.
- UNLIKELY: does not have temporal relationship to intervention, could readily have been produced by the subject's clinical state, environmental, or other interventions, does not reappear or worsen with reintroduction of intervention.
- POSSIBLY: bears relation to timing of medication, similar to symptoms or signs expected in the disease process, does not recur on rechallenge.
- PROBABLY: bears clear relation to timing of medication, distinct from symptoms or signs expected in the disease process, does not recur on rechallenge.
- DEFINITELY: bears clear relation to timing of medication, distinct from symptoms or signs expected in the disease process, occurs on rechallenge.

The expected adverse events related to administration of PD-0325901 are listed in Section 6.1.5. All other adverse events not attributed to study drug will be considered unexpected. Adverse events attributable to study drug will be reported if the adverse events are at an intensity that is more severe than previously documented or considered significant by the investigator.

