The two main peripheral nerve tumors in patients with NF1 are neurofibroma, a benign tumor, and malignant peripheral nerve sheath tumor (MPNST). These tumors are related in that most MPNSTs arise by malignant transformation of neurofibroma. Based on a recent study, the life-time risk of developing MPNST in patients with NF1 is 8-13%⁴. There are multiple types of neurofibromas including localized cutaneous neurofibroma, localized intraneuronal neurofibroma, diffuse neurofibroma, massive soft tissue neurofibroma and plexiform neurofibroma. Plexiform neurofibromas are benign nerve sheath tumors that grow along the length of nerves and involve multiple branches of a nerve. These tumors are usually diagnosed early in life, may be multiple and might develop throughout life. Early childhood, puberty and childbearing age in females are considered to be the periods of greatest risk for disease progression⁵. Between 20-44% of individuals with NF1 develop plexiform neurofibromas⁶. These tumors may cause significant disfigurement, as well as compression of vital structures. As examples, plexiform neurofibromas may infiltrate the orbit and displace the globe and compromise vision; paraspinal tumors (also referred to as dumbbell lesions) can compress the spinal cord and cause paralysis; tumors in mediastinum may compress the trachea or great vessels; and tumors of the extremities can cause local nerve infiltration, progressive neurologic deficit and often unremitting pain⁵.

[figure not shown]

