Among 13 subjects enrolled on a 15 mg bid 3 weeks on/1 week off schedule (Schedule 1- see Table 2), the most frequently reported treatment-related adverse events (AEs) were gastrointestinal disorders (11 subjects, 84.6%), including diarrhea (7 subjects, 53.8%), nausea and vomiting (each in 6 subjects, 46.2%), and dry mouth (2 subjects, 15.4%). Seven of 13 subjects (53.8%) experienced at least one Grade 3, treatment-related AE according to the CTCAE criteria. No subjects experienced treatment-related Grade 4 or Grade 5 AEs. Treatment-related Grade 3 AEs included inappropriate antidiuretic hormone secretion, diarrhea, pneumonia, hypocalcemia, confusional state, hallucination, dyspnea, lung infiltration, and rash, each in 1 subject (7.7%).

Among 21 subjects enrolled on a 15 mg bid 5 days on/2 days off for 3 weeks followed by 1 week off schedule, the most frequently reported AEs were also gastrointestinal disorders, which occurred in all subjects (n = 21, 100%). These AEs included diarrhea (16 subjects, 76.2%), vomiting (7 subjects, 33.3%), nausea (6 subjects, 28.6%), constipation (4 subjects, 19.0%), and abdominal pain, abdominal pain (upper), and dry mouth, each experienced by 3 subjects (14.3%). One subject (4.8%) experienced dyspepsia during this study. 6 of 21 subjects (28.6%) experienced at least one treatment-related Grade 3 AE, and 3 subjects (14.3%) experienced at least one treatment-related Grade 4 AE. Treatment-related Grade 3 AEs included atrial flutter, diarrhea, hiatus hernia, bronchitis, alanine aminotransferase increased, aspartate aminotransferase increased, syncope, confusional state, dyspnea, hypoxia, and hypotension, each in 1 subject (4.8%); and fatigue and dehydration in 2 subjects (9.5%). Treatment-related Grade 4 AEs included diarrhea, dehydration, pneumonia aspiration, pulmonary embolism, pulmonary hypertension, and deep vein thrombosis, each in 1 subject (4.8%).

Table 1 Adverse drug reactions occurring in patients receiving PD-0325901 in Phase 1/2 Studies*

System Organ Class	Adverse Reaction
Eye Disorders	Retinal vein occlusion, retinal hemorrhage, optic ischemic neuropathy
Nervous system disorders	Dizziness, paresthesia
Gastrointestinal disorders	Diarrhea
Skin and subcutaneous tissue disorders	Rash
Musculoskeletal and connective tissue disorders	Muscle disorder (neck drop), muscular weakness
Psychiatric disorders	Confusional state

*Table 7-1 in PD-0325901 Investigator Brochure September 2012

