8.3 Toxicities Requiring Removal From Protocol Therapy

Any toxicity defined in section 8.1 or 8.2 that is at least possibly related to study medication that recurs on a reduced dose of PD-0325901. No subject may be dose-reduced more than once.

Any \geq Grade 3 toxicity that is at least possibly due to study drug that does not resolve to \leq Grade 1 within 2 weeks requires removal from protocol therapy.

Development of retinal vein occlusion will also require removal from protocol therapy

Development of glaucoma, intraocular pressure >21 mmHg, or any other significant abnormality on ophthalmic examination (performed by an ophthalmologist) while on study treatment will require removal from protocol therapy. Ophthalmological findings secondary to long-standing Optic Pathway Glioma such as optic nerve pallor or strabismus will NOT be considered significant for the purposes of the study.

The study chair or co-chair should be contacted for any questions regarding toxicity.

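### Section 10.3 has no attribution category for a disease-like toxicity that recurs on restart, which conflicts with the first removal rule in Section 8.3

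*Combined protocol and SAP*

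**What the plan says.** Section 10.3 defines five levels of relationship to study drug, three of which count as related. The lowest of these three reads "POSSIBLY: bears relation to timing of medication, similar to symptoms or signs expected in the disease process, does not recur on rechallenge". The middle level, PROBABLY, keeps the non-recurrence condition but asks for a clear timing relation and for an event unlike the disease. The highest level differs from the middle one only in its final clause, which turns on recurrence: "DEFINITELY: bears clear relation to timing of medication, distinct from symptoms or signs expected in the disease process, occurs on rechallenge".

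At the other end of the scale stands "UNRELATED: bears no relation to timing of medication, similar to symptoms or signs expected in the disease process, does not recur on rechallenge". The level above it, UNLIKELY, also denies a temporal relationship and requires that the event did not return or worsen when the drug was reintroduced.

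Sections 8.1 and 8.2 hold the drug for qualifying toxicity that is at least possibly related, and allow restart at a reduced dose after recovery. The first rule in Section 8.3 then requires removal when a toxicity of either kind is described by these words: "at least possibly related to study medication that recurs on a reduced dose of PD-0325901". Section 12.3 stops accrual pending DSMB review if more than 2 of the first 10, or 4 or more of the first 15, subjects are removed for toxicity under Section 8.3.

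**The concern.** Return of an event on restart is ordinarily evidence that the drug caused it. In 10.3, for an event that resembles the disease, it does the opposite: it takes the event out of POSSIBLY and offers nothing in its place. Restart after a hold is a normal step under 8.1 and 8.2, and recurrence after restart is what the first rule in 8.3 looks for. That rule therefore depends on a classification that 10.3 does not provide for this kind of event.

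The overlap between drug effect and disease is foreseeable. Table 1 in Section 6.1.5 lists "Muscle disorder (neck drop), muscular weakness" and paresthesia among the adverse drug reactions. Section 2.1 describes tumors of the extremities as causing "progressive neurologic deficit and often unremitting pain". New or worse weakness in a treated subject could plausibly be either.

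At stake is whether such a recurrence is consistently called related, and so whether the removal enters the safety count. The threshold is 3 in the first 10 subjects, so one subject can decide whether the DSMB review is triggered. Relatedness also governs which serious, unexpected events are forwarded to the FDA (Section 10.5).

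**Working it through.** **1. Match event patterns to categories.** Take an event with a clear timing relation, so that the timing clause of all three related categories is met. Cross disease-likeness with the outcome of restart:

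| Event | Did not recur on restart | Recurred on restart | Never restarted |
|---|---|---|---|
| Resembles NF1 | POSSIBLY | **none** | POSSIBLY if no restart counts as no recurrence; otherwise none |
| Distinct from NF1 | PROBABLY | DEFINITELY | PROBABLY if no restart counts as no recurrence; otherwise none |

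The disease-like, recurrent cell is empty under either reading of the never-restarted column. It fails POSSIBLY on recurrence, PROBABLY on both recurrence and resemblance, and DEFINITELY on resemblance. UNRELATED and UNLIKELY fail on both timing and recurrence. The disease-like row is the same if the timing relation is present but not clear.

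**2. Set this against the first rule in 8.3.** The rule needs (a) at least possibly related and (b) recurrence on the reduced dose. For a disease-like event, (a) can be met only through POSSIBLY, and POSSIBLY requires that (b) is false. The two conditions exclude each other.

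**3. Check the boundary that these removals feed.** With X binomial and a true rate of 10%:

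- P(X ≥ 3 of 10) = 1 − (0.3487 + 0.3874 + 0.1937) = 0.0702. The plan states 0.07.
- P(X ≥ 4 of 15) = 1 − (0.2059 + 0.3432 + 0.2669 + 0.1285) = 0.0556, rounding the final figure from unrounded terms. The plan prints 0.055.
- Chance of at least 3 of 10 at true rates of 10, 20, 25, 30, 35 and 40%: 7.0, 32.2, 47.4, 61.7, 73.8 and 83.3%. The plan states 7, 32, 47, 62, 74 and 83%.

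The boundary arithmetic reproduces. The question is only which events enter the count.

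**4. Identify which 8.3 removals depend on attribution.** The first two rules do (recurrence on the reduced dose; Grade 3 or higher toxicity not resolved within 2 weeks). Removal for retinal vein occlusion, glaucoma, raised intraocular pressure or another significant ophthalmic abnormality carries no drug-relatedness condition. Only the recurrence rule meets the certain gap in step 1.

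**The case against.** The strongest reply is that attribution is made at first occurrence, before any restart. At that point the event can be called POSSIBLY, and nothing says that recurrence cancels the call. Section 8.2 adds that non-hematological toxicity at the reduced dose leads to removal, without asking for fresh attribution, and Section 10.4 lets the investigator remove a subject on clinical judgment. A sensible investigator would probably remove the subject. This stands as a limit on the harm. It does not remove the conflict: the first rule in 8.3 restates relatedness for a toxicity that recurs, 10.3 has no entry for that event, and removal on judgment under 10.4 is not, on its text, removal under 8.3, so it may not be counted.

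Three stronger readings are tempting and are not supported:

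- *Any event never rechallenged has no related category.* This holds only if a rechallenge result must exist. An event not rechallenged can equally be read as one that did not recur. The text does not settle it, so this is an ambiguity.
- *Removal and the boundary count only related events.* The ophthalmic removals in 8.3 need no attribution and feed the same count, and any retinal vein occlusion halts enrollment by itself (Section 12.3).
- *Drug-related events would drop out of the safety tables.* Section 10.4 records all adverse events whatever their suspected cause, and Section 12.3 plans AE and SAE tabulations with no relatedness filter.

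**Conclusion.** The conflict between 10.3 and 8.3 is real and narrow. One of the six patterns in the table, the disease-like event that recurs on restart, has no category under any reading. Two more, the never-restarted patterns, are ambiguous.

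The conclusion rests on treating restart after a hold as a rechallenge, a term the protocol does not define. If reduced-dose restart were not a rechallenge, the event would fall under the never-rechallenged ambiguity instead.

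The size of the effect cannot be estimated from the documents. A reader might try to quantify it: if the true removal rate were 30% and one in five removals went uncounted, the effective rate would be 0.30 × 0.80 = 0.24, and the chance of reaching 3 of 10 would fall from 62% to 44%. The arithmetic is right, but it does not measure this gap. The 30% is one row of the plan's operating table and not an expected rate, the one in five has no source, and the loss is applied to all removals, including ophthalmic ones that need no attribution and distinct recurrent events that fit DEFINITELY.

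The point is worth correcting because it is an internal contradiction in a safety rule and costs almost nothing to remove.

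**What to change.** In Section 10.3, keep the timing and disease-resemblance clauses and change only the rechallenge clauses:

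- **POSSIBLY:** applies whether or not the event recurs on rechallenge, and whether or not rechallenge was done.
- **PROBABLY:** applies if the event did not recur on rechallenge, or if rechallenge was not done.
- **DEFINITELY:** unchanged.

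Every disease-like cell in the table then falls under POSSIBLY. Distinct events fall under PROBABLY or DEFINITELY without overlap. A recurring disease-like event is at least possibly related, which is all that 8.3 needs. It should not be assigned to PROBABLY, which requires the event to be distinct from the disease. Nor should PROBABLY lose its rechallenge condition altogether, because it would then overlap with DEFINITELY.

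The cost is two lines in 10.3 and matching instructions on the adverse event form. No data are added, and no dosing or removal rule changes.

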10.4 Reporting Procedures for All Adverse Events

All observed or volunteered adverse events, regardless of suspected causal relationship to study drug, will be recorded as Adverse Events in the case report forms and submitted to the Operations Center within 2 weeks of completion of each treatment course. Events involving adverse drug reactions, illnesses with onset during the study, or exacerbation of pre-existing illnesses should be recorded. Objective test findings (e.g., abnormal laboratory test results) should also be recorded.

It will be left to the investigator's clinical judgment whether or not an adverse event is of sufficient severity to require that the subject should be removed from treatment. A subject may also voluntarily withdraw from treatment due to what he or she perceives as an intolerable adverse event. If either of these occurs, the subject will be given appropriate care under medical supervision until symptoms cease or until the condition becomes stable.

Adverse events will be assessed by the treating investigator for relationship to the study drug (unrelated, unlikely, possible, probable, or definitely related).

